#### Pharmacokinetic analysis

Descriptive statistics of trough concentrations of empagliflozin will be presented for patients, where PK data is available.

### **7.7 EXTENT OF EXPOSURE**

There will be three methods of calculating exposure:

- a. First intake to last intake of study drug, including off-treatment periods
- b. First intake to last intake of study drug, excluding off-treatment periods
- c. Overall observational period (randomisation until end of follow-up for vital status, see censoring for all-cause mortality in [Section 6.8.3](#))

Descriptive statistics tables with mean, standard deviation (SD), median and range of the number of days a patient was on treatment will be provided. These tables will also provide the sum-total of the time (in years) that all patients were on treatment. The table will be repeated for diabetes status (2 cat.) and eGFR (5 cat.).

Frequency tables of number and percentage of patients belonging to categorical ranges of exposure weeks will be provided as well. Following are the categories of exposure-ranges (in weeks): 0 to <12 weeks,  $\geq 12$  to <26 weeks,  $\geq 26$  to <52 weeks,  $\geq 52$  to <78 weeks,  $\geq 78$  to <104 weeks,  $\geq 104$  to <156 weeks,  $\geq 156$  weeks. Categorical ranges may be adapted based on the actual duration of the study.

### **7.8 SAFETY ANALYSIS**

The safety analysis will be based on the treated set (TS), treatment will be evaluated as randomised.

The AE analysis will include all adverse events (including outcome events as reported by the investigator).

While tables will generally display results by randomised treatment, listings will reflect whether a measurement/AE occurred on or off treatment.

### **7.8.1 Adverse events**

Unless otherwise specified, the analyses of adverse events will be descriptive in nature and will be based on the number of patients with AEs and not on the number of AEs.

AEs will be coded using the most recent version of the Medical Dictionary for Regulatory Activities (MedDRA) coding dictionary.

Definitions of Boehringer Ingelheim customized MedDRA Queries (BICMQs) for new MedDRA versions are maintained by the BI dictionary maintenance group.

For analysis multiple AE occurrence data on the CRF will be collapsed into an AE provided that all of the following applies:

- All AE attributes are identical (including LLT, intensity, action taken, therapy required, seriousness, reason for seriousness, relationship, outcome, AE of special interest and also additional information of specific AEs or AESIs such as source of sepsis (urinary tract or not) or type of genital infection (fungal balanitis or vulvovaginitis versus other than fungal balanitis or vulvovaginitis)).
- The occurrences were time-overlapping or time-adjacent (time-adjacency of 2 occurrences is given if the second occurrence started on the same day or on the day after the end of the first occurrence).

For further details on summarization of AE data, please refer to [\(2\)](#), [\(12\)](#).

#### **7.8.1.1 Assignment of AEs to treatment**

The analysis of adverse events will be based on the concept of treatment emergent adverse events. That means that all adverse events occurring between first drug intake till 7 days after last drug intake will be assigned to the randomised treatment. All adverse events occurring before first drug intake will be assigned to 'pre-treatment' and all adverse events occurring after last drug intake + 7 days will be assigned to 'follow-up'.

In Section 15.3 general AE analyses tables will present only on-treatment AEs (applying the rule of 7 days for assignment as on-treatment) for the treatments groups (exceptions for urinary tract malignancies, hepatic events, lower limb amputations and bone fractures as well as adjudicated events see below). When looking at BICMQs or standardized MedDRA queries (SMQs) and including all AEs up to completion of the trial, the time at risk for each patient will be calculated up to the individual day of trial completion (see [section 6.8](#)).

Appendix 16.1.13.1 will include an analysis (overall summary table, frequency of AEs by system organ class (SOC) / preferred term (PT), frequency of serious adverse events (SAEs) by SOC/PT) where AEs and SAEs are assigned to the following phases: Screening, each

treatment group, post-treatment for each treatment group.

The tables presenting frequency of AEs by SOC/PT and frequency of SAEs by SOC/PT will be repeated in Section 16.1.13.1 with treatment-specific post-treatment phase included, hereby also incidence rates for the post-treatment phase will be presented.

For listings, AEs will be assigned to one of the treatment phases of Screening, Placebo, Empa 10, Placebo post-treat, Empa 10 post-treat, post-study.

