4.2.2 Restrictions

The use of any SGLT-2 inhibitors or combined SGLT-1 and 2 inhibitors, except the blinded trial medication, is prohibited during the course of the trial. This does not include the 30 day period between the EOT and the Follow Up Visit occurring at the study close-out (see [section 6.2.3](#)). If any restricted treatment is given during the conduct of the trial, the trial medication can be discontinued temporarily, or if needed permanently.

If the patient is in need of any additional treatment during this period, this may be given at the discretion of the Investigator. The patient can still remain on trial medication.

WOCBP must use the contraception methods as described in the patient information.

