A3.35	History of Ketoacidosis	Exclusion criterion #17 met	None
A3.36	Gastrointestinal (GI) surgery or GI disorder that could interfere with study medication absorption in the investigator's opinion	Exclusion criterion #19 met	None
A3.37	Documented or active malignancy	Exclusion criterion #20 met	None
A3.38	Life expectancy of <1 years in the opinion of the investigator	Exclusion criterion 21 met	None
A3.39	Intake of restricted medications or any drug considered likely to interfere with the safe conduct of the trial	Exclusion criterion #22 met	None
A3.40	Treatment with any SGLT-2 inhibitor or SGLT-1 and 2 inhibitor	Exclusion criterion #23 met	None
A3.11	Intake of an investigational drug in another trial within 30 days prior to intake of study medication in this trial	Exclusion criterion #24 met	None
A3.41	Known allergy or hypersensitivity to empagliflozin	Exclusion criterion #25 met	None
A3.13	Relevant alcohol or drug abuse and condition affected study compliance	Exclusion criterion #26 met	None
A3.12	Specific exclusion criterion for premenopausal women violated	Exclusion criterion #27 met	None
A3.14	Any other clinical condition unsafe for participation	Exclusion criterion #28 met	None
A3.53	Recently implanted ICD/CRT or intent to implant	Exclusion criterion #29 met	None

Table 6.2: 1 Important protocol deviations (cont.)

Category / Code	Description	Requirements	Excluded from
B	Informed consent		
B1	Informed consent not available/not done	Informed consent date missing or inclusion criterion #9 met	All
B2	Informed consent too late	Informed consent date was after Visit 1	None
C	Trial medication and randomisation		
C1.02	Incorrect trial medication taken	Wrong medication taken for more than 20% of the overall treatment duration Can only be finally judged after data base lock (DBL) since unblinding information is required.	None
D	Concomitant medication		
D2.02	Use of prohibited medication	Use of SGLT-2 or combined SGLT-1 and 2 inhibitors after randomization but before the EOT visit occurring at study close out	None

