### 6.3 SUBJECT SETS ANALYSED

The following patient sets are defined

- *Screened Set (SCR)*  
Consists of all patients screened for the trial, with informed consent given and who completed at least one screening procedure at Visit 1.
- *Randomised set (RS)*  
This patient set includes all randomised patients, whether treated or not.
- *Treated set (TS)*  
This patient set includes all patients who were dispensed study medication and were documented to have taken at least one dose of investigational treatment.
- *Treated Set-Follow-up (TS-FU)*  
All patients in the TS, for whom a follow-up visit was performed (i.e. values of planned assessments- KCCQ, EQ-5D, vital signs or lab data reported) between 23 and 45 days after last intake of study medication.

The TS-FU does not include patients, where no planned measurements were taken, which may happen in case of telephone FU visits. Patients with intake of open label SGLT-2 inhibitor between their EOT and FU visit are also excluded from the TS-FU set.

- *Pharmacokinetic Set (PKS)*  
This patient set includes all evaluable patients of the treated set who provide at least one observation for at least one further PK endpoint of Cpre,ss,N for empagliflozin.

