#### Events leading to lower limb amputation

A frequency table of patients with AEs leading to lower limb amputation as identified by the investigator by treatment, primary SOC and preferred term will be provided.

A separate table for AEs leading to lower limb amputation which are leading to discontinuation will be presented.

For events leading to lower limb amputations in addition to the ‘7-day-on-treatment approach’ all adverse events that occurred between first study drug intake up to trial completion will be presented (following censoring rules like non-fatal outcome events). For both approaches, SAEs will be presented.

Lower limb amputations (up to trial completion) will additionally be summarised by renal function, level of first amputation, reason for first amputation, history of PAOD, previous amputation and status of DM at baseline (DM / no-DM).

Patients with lower limb amputation will be listed.

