			Section 7.6	Responder analyses (improvement and deterioration of 5 points or more from baseline) for KCCQ clinical summary score, clinical symptoms and physical limitations domain was added.
			9.3	Clarification of diabetes definition
			Throughout and section 9.6	Include wording from the protocol to the TSAP and clarify sample size
Revised	19-NOV-2019		6.2, 6.3	Changes to IPD D2.02 and TS-FU set to reflect change in CTP with regards to open label SGLT-2 inhibitor use after EOT visit
			6.4, 7.6, 10	Typos corrected
Revised	19-JUN-2020		6.8.3, 7.8.1.1	Clarifications with regard to censoring rules
			7.4.2, 7.5.1.1	Addition of sensitivity analyses for COVID-19
			7.8.1.4	Insert word “narrow” for clarification
			9.4, 7.4.4	Add baseline eGFR (5 categories) to subgroups

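### Post-treatment AE tables and rates count open-label SGLT-2 inhibitor users under their randomised arm, although the SAP excludes the same patients from TS-FU

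*SAP*

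**What the plan says.** Protocol 4.2.2 prohibits SGLT-2 and combined SGLT-1/2 inhibitors other than trial medication during the trial, and then makes an exception: "This does not include the 30 day period between the EOT and the Follow Up Visit occurring at the study close-out".

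The SAP responded in two places. The follow-up set was narrowed: "Patients with intake of open label SGLT-2 inhibitor between their EOT and FU visit are also excluded from the TS-FU set" (SAP 6.3). Important protocol deviation D2.02 was limited to "Use of SGLT-2 or combined SGLT-1 and 2 inhibitors after randomization but before the EOT visit occurring at study close out" (SAP 6.2), so use after the close-out EOT is not recorded as a deviation. The history table (SAP 10) describes that revision as "Changes to IPD D2.02 and TS-FU set to reflect change in CTP with regards to open label SGLT-2 inhibitor use after EOT visit" and lists only Sections 6.2 and 6.3 for it.

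The safety analysis has no matching rule. SAP 7.8 states: "The safety analysis will be based on the treated set (TS), treatment will be evaluated as randomised". Under SAP 7.8.1.1, AEs starting more than 7 days after last study drug intake go to follow-up. The tables by SOC and preferred term are repeated in 16.1.13.1 "with treatment-specific post-treatment phase included, hereby also incidence rates for the post-treatment phase will be presented", and the listings label these phases *Placebo post-treat* and *Empa 10 post-treat*. SAP 7.8.1.7 derives post-treatment time at risk as for the on-treatment phase but with a new start date, and mentions no stop at open-label intake.

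**The concern.** Protocol 3.2 regards the 30-day follow-up as long enough to assess adverse events after trial medication is stopped. A post-treatment rate that mixes time off the class with time on a commercially supplied drug of the same class does not answer that question cleanly.

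Take a former placebo patient who starts an open-label SGLT-2 inhibitor just after EOT and has a genital infection on day 20. Protocol 1.2.3 reports more genital infections with empagliflozin. The event is tabulated under *Placebo post-treat*. A former empagliflozin patient who does the same is tabulated as post-treatment while still exposed to the class. The SAP treats this exposure as a reason for exclusion in one planned output and leaves it invisible in another.

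**Working it through.** **Text check.** Three other parts of the SAP might have covered the gap.

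- SAP 7.8.1.6 (wrong medication) adds a table by treatment actually taken. It is framed for wrong trial medication, does not mention open-label use, and credits off-treatment periods to the preceding treatment.
- SAP 7.2 summarises therapies taken after baseline, so overall uptake may be visible, but it is not linked to AEs.
- SAP 7.8.1.5 limits the adjudicated ketoacidosis tables to 7 days after treatment stop, so those tables are largely protected, but the general post-treatment tables are not.

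The gap therefore stands on the text. The users can be identified: concomitant therapy is recorded at the follow-up visit (Protocol Flow Chart and 6.2.3), and the TS-FU exclusion already needs that information.

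**Size.** The plan states no figure to reproduce. Let the placebo post-treatment AE rate be λ off the class and Rλ on it. Let s be the share of all placebo post-treatment time that falls in the close-out window, and f the share of that window spent on open-label drug. Then

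rate = λ[(1 − sf) + sfR] = λ[1 + s·f·(R − 1)].

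The factor s is needed because the same row pools patients who stopped study drug early. They are followed to trial end (Protocol 3.3.4.1), and the exception in Protocol 4.2.2 does not apply to them before close-out.

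Inputs:

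- From the documents: about 3600 patients randomised 1:1, so 1800 per arm (SAP 9.6, Protocol 7.6); 30 − 7 = 23 days per completer (follow-up visit at 30 days, AEs assigned to follow-up after 7).
- Assumed: 75 to 85% on study drug at close-out; early stoppers off drug for 6 to 12 months on average; the same background rate in both groups.

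Close-out person-time per arm:

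- 85% on drug: 1800 × 0.85 × 23/365.25 = 96 patient-years
- 75% on drug: 1800 × 0.75 × 23/365.25 = 85 patient-years

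Early-stopper person-time per arm:

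- 1800 × 0.15 × 0.5 year = 135 patient-years
- 1800 × 0.25 × 1 year = 450 patient-years

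This gives s = 96/(96 + 135) = 0.42 at the high end and 85/(85 + 450) = 0.16 at the low end.

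With R = 3 (assumed), the factor is 1 + 2·s·f:

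| f (assumed) | s = 0.16 | s = 0.42 |
|---|---|---|
| 0.05 | 1.016 | 1.042 |
| 0.20 | 1.064 | 1.168 |
| 0.30 | 1.096 | 1.252 |

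With open-label users removed, f = 0 and the factor is 1 by construction.

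**The case against.** **The affected tables are secondary.** Safety is descriptive and no hypothesis is tested (Protocol 7.3.4). The general Section 15.3 tables show on-treatment AEs under the 7-day rule, so a day-20 event does not enter them. This stands. The one leak is an event on open-label drug within 7 days of last study drug intake, which counts as on-treatment for the randomised arm.

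**TS-FU has a different purpose.** It supports changes between the last on-treatment value and follow-up in eGFR, NT-proBNP and similar measures (SAP 7.6), where resumed class exposure would mask reversal. AE phases are defined by study drug intake, and the SAP does not say that the post-treatment phase estimates off-drug risk. This weakens the charge of inconsistency. It does not remove the interpretive problem, given the purpose that Protocol 3.2 assigns to follow-up.

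**A cut at open-label start has its own faults.** Starting open-label drug is a post-randomisation choice, so stopping time at risk there may be informative. Partial therapy dates are imputed to mid-interval, for example day 15 of the month (SAP 6.6.2), which could misorder intake and event inside a 23-day window. Both points stand and shape the fix.

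**Details may sit elsewhere.** SAP 7.8.1 refers to internal AE guidance that is not available here. Only the SAP text could be checked.

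**Conclusion.** The gap is real and modest. Under R = 3 and s = 0.16 to 0.42, the placebo post-treatment rate is inflated by about 2 to 4% at f = 0.05, 6 to 17% at f = 0.20 and 10 to 25% at f = 0.30. Uptake, class rate ratio and close-out share are all assumptions. If uptake is similar in both arms, the formula applies to each, and the level of the rates suffers more than their ratio.

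Three stronger readings are tempting, and the documents do not support them.

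- A reader might apply 1 + f(R − 1) to the whole row, giving +10%, +40% and +60% at the same f. That holds only if all post-treatment time is close-out time (s = 1), which ignores the early stoppers pooled in the row.
- A reader might infer that the main safety comparison is compromised. Apart from the 7-day leak, the Section 15.3 general tables exclude this period.
- A reader might extend the point to the 30-day hepatic displays and to the fracture, urinary tract malignancy and amputation analyses, since for amputation "all adverse events that occurred between first study drug intake up to trial completion will be presented". These supplement the 7-day approach. For the analyses to trial completion, the window is at most about 30 days of the 20 to 38 months implied by 18 months' accrual plus 20 months' follow-up (Protocol 7.7), or 3 to 5% of the time. At f = 0.20 and R = 3 the change is 2 × 0.20 × 0.03 to 0.05, about 1 to 2%. The documents show no class effect for hepatic events or malignancy that would make it larger.

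Neither the primary conclusion nor the permission in Protocol 4.2.2 is in question.

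**What to change.** Treat this as a cheap improvement.

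1. Keep the as-randomised post-treatment tables as planned.
2. In SAP 7.8.1.1 and 7.8.1.7, add a repeat of the post-treatment AE and SAE tables and incidence rates that excludes patients who took open-label SGLT-2 inhibitor between EOT and follow-up, using the TS-FU criterion. Where the start date is complete, an alternative is to end time at risk the day before first intake. Exclusion is the safer default because it does not depend on imputed dates.
3. Flag open-label use in the AE listings.

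The cost is a few lines of SAP text, one patient-level flag that TS-FU already requires, and one repeated set of appendix tables. The downside is slightly less post-treatment person-time and a subset selected by a post-randomisation choice, so the repeat should be labelled supplementary. The hepatic, fracture, amputation and malignancy analyses need no change on this account.

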#### 7.8.1.2 AE summaries

An overall summary of adverse events will be presented.

The frequency of patients with adverse events will be summarised by treatment, primary system organ class and preferred term. Incidence rates as defined in [Section 7.8.1.7](#) will generally be included. AEs will also be reported by intensity (without incidence rates). Separate tables will be provided for patients with adverse events of special interest (AESIs), for patients with serious adverse events, for patients with drug related serious AEs, for patients with fatal events, for patients with AEs leading to discontinuation, and for patients with drug-related AEs.

The frequency of patients with adverse events occurring with incidence in preferred term greater than 2% by treatment will also be presented.

Overall AE summaries, AEs by SOC and PT, SAEs and AEs leading to discontinuation will additionally be investigated by subgroups as outlined in [Table 6.4: 1](#).

Fatal AEs will be summarized up to end of the trial, also separately for those adjudicated as CV and those adjudicated non-CV cause.

The system organ classes will be sorted according to the standard sort order specified by the European Medicines Agency (EMA), preferred terms will be sorted by frequency (within system organ class).

Additionally, the following analyses will be reported in Appendix 16.1.13.1 for disclosure on EudraCT and clinicaltrials.gov:

- Frequency [N(%)] of patients with non-serious adverse events occurring with incidence in preferred term greater than 5% by treatment,
- Adverse Events per arm for disclosure on EudraCT by treatment”
- Non-serious Adverse Events for disclosure on EudraCT by treatment
- Serious Adverse Events for disclosure on EudraCT by treatment

For further details, see also [\(13\)](#).

#### 7.8.1.3 Adverse events of special interest (AESIs)

##### Hepatic injury

Adverse events reported as AEs of special interest relating to hepatic injury as specified in the protocol will be summarised.

Additionally Hepatic injury AEs will be summarized based on an SMQ based definition. From SMQ Drug related hepatic disorders (20000006) the following narrow sub-SMQs will be used:

- Narrow sub-SMQ Liver related investigations, signs and symptoms (20000008)
- Narrow sub-SMQ Cholestasis and jaundice of hepatic origin (20000009)
- Narrow sub-SMQ Hepatitis, non-infectious (20000010)
- Narrow sub-SMQ Hepatic failure, fibrosis and cirrhosis and other liver damage-related conditions (20000013)

A table with frequencies of patients with these AEs by treatment, primary SOC and preferred term will be provided. This presentation will be repeated by DM status at baseline (DM vs no DM). Hepatic injury SAEs and hepatic injury AEs leading to disc based on the above SMQ definition will be presented.

In addition to the '7-day-on-treatment approach', a '30-day-on-treatment approach' will be presented for the overall hepatic adverse events based on the SMQ definition.

Patients with hepatic injury will be listed.

For presentations on adjudicated hepatic events, refer to [Section 7.8.1.5](#).

#### Decreased renal function

Adverse events reported as AEs of special interest relating to decreased renal function as specified in the protocol will be summarised.

A frequency table of patients with AEs of acute renal failure by treatment, primary SOC and preferred term will additionally be provided based on the narrow standardized MedDRA query (SMQ) Acute renal failure (20000003).

This presentation will be repeated by the subgroups as outlined in [Table 6.4: 1](#). SAEs and AEs leading to disc based on the SMQ Acute renal failure (20000003) will be presented.

In addition, frequency tables will be produced for patients with elevated creatinine  $\geq 2$  x baseline and  $> 1$  x upper limit of normal (ULN).

Patients with decreased renal function will be listed.

#### Ketoacidosis

A frequency tables of patients with AEs related to ketoacidosis will be presented by treatment, primary SOC and preferred term for investigator defined cases and for the broad and narrow BICMQ definition of diabetic ketoacidosis.

For the narrow BICMQ diabetic ketoacidosis (DKA), AEs leading to discontinuation and an analysis by sex and diabetes status (type 1 diabetes, type 2 diabetes, pre-diabetes and normal (no pre-diabetes)) will be presented.

For the broad BICMQ diabetic ketoacidosis (DKA), SAEs will be presented.

For presentations on adjudicated events, refer to [Section 7.8.1.5](#).

Patients with DKA based on the narrow and broad BICMQ or investigator defined ketoacidosis will be listed.

